4.11.2. Intervention Assessment

Information related to all interventions that are performed for an SSC will be documented at all post-surgery visits including unscheduled visits. Information collected will include but is not limited to:

- Date of intervention
- Type of interventions
- Types of interventions may include open surgical or percutaneous drainage, debridement, excision, or re-operation.

4.11.3. Healthcare Utilization Assessment

Information related to additional hospital procedures and/or follow-up care after the subject's TKA revision during the study period will be documented at all post-surgery visits, scheduled or unscheduled. Data to be collected will include:

- Relatedness to the TKA revision
- Duration of stay for TKA revision
- Length of hospital stay (days)
- Days in ICU
- Re-admission after TKA revision (yes/no)
- Length of hospital stay (days)
- Days in ICU
- Number of home health visits after hospital discharge
- Number of clinic visits after hospital discharge
- Number of rehab/physical therapy visits

4.12. Pain Assessment

Subjects will answer two questions asking them, on a scale from 0 (no pain) to 10 (pain as bad as you can imagine), to recall and rate their worst and average pain in the last 24

hours. Subjects will answer these questions prior to the TKA revision, at the earlier of discharge or 24 hours (\pm 2 hours) after the TKA revision, and at the weekly study treatment visits. Subjects will document whether they completed the assessment before or after consultation with the Investigator. At the weekly study treatment visits, the subject will record whether the pain assessment was performed before or after the dressing removal.

4.13. Patient Reported Outcomes (PRO) Assessments

4.13.1. Knee Injury and Osteoarthritis Outcome Score (KOOS)

The KOOS is a 42-item disease-specific patient reported outcome (PRO) measure designed to assess short-term and long-term symptoms and function in subjects with knee injury and osteoarthritis. The KOOS has been validated for several orthopaedic interventions including total knee replacement.¹⁸⁻²¹ The KOOS consists of five subscales:

- Knee-related Quality of Life,
- Function in Sport and Recreation,
- Function in Daily Living,
- Pain, and
- Other Symptoms.

Intended for use over short-term or long-term intervals to assess changes from visit to visit, subjects will be asked to complete the KOOS questionnaire on their own at the Screening, weekly study treatment visits, Midterm Follow-up, and the Long Term Follow-up visits.

Subjects will record whether they completed the assessment at a particular visit before or after consultation with the Investigator.

4.13.2. Patient-Reported Outcomes Measurement Information System (PROMIS) Global-10 Assessment

The PROMIS Global-10 is a generic health assessment that measures the physical, social, and emotional health of individuals and is often used for those living with chronic conditions.

Subjects will be asked to complete the PROMIS Global-10 questionnaire on their own at the Screening, weekly study treatment visits, Midterm Follow-up, and Long Term Follow-up visit.

Subjects will record whether they completed the assessment at a particular visit before or after consultation with the Investigator.

4.14. Concomitant Medications

Concomitant medications will be collected from the time of informed consent through the Long Term Follow-up visit. The medication name, start date, end date, and indication will be reported.

Special consideration should be given to report medications given to treat SSCs or that may affect the healing process such as:

- all antimicrobial medications taken by the subject from time of informed consent throughout the duration of the study especially IV, which may be given to the subject for pre-op prophylaxis within 24 hours of surgery followed by a course of oral antibiotics post-TKA revision
- opioid medications (e.g., morphine) taken by the subject within 14 consecutive days after randomization
- immunosuppressants
- corticosteroids
- non-steroidal anti-inflammatory drugs (NSAID)
- anti-coagulants (e.g., Lovenox, aspirin, Coumadin)
- all medications with a prophylactic indication
- all medications the subject is given to treat an AE during the study

4.15. Prohibited Procedures and Treatments

Subjects who undergo a subsequent surgery involving the initial TKA incision within 90 days must withdraw from the study.

Subjects who receive a subsequent TKA revision on the same knee within 90 days of the study revision must withdraw from the study prior to the procedure. Sites will record any SSCs that occur prior to the subsequent TKA revision and document the revision as the reason for the withdrawal from the study.

In the absence of an SSC, subjects receiving cross-over therapy after completing the original study treatment (ie, therapy from the arm in which the subject was not initially treated) must withdraw from the study.

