3.2. Design Summary

This post-market, prospective, randomized, open-label, multicenter, controlled study will evaluate the effectiveness of closed incision negative pressure therapy (ciNPT) compared to standard of care (SOC) surgical dressing in reducing the surgical site complications (SSCs) in subjects with revision of a failed total knee arthroplasty (TKA).

The study will randomize approximately 440 subjects from approximately 15 sites in a 1:1 ratio to receive either ciNPT or SOC after a revision TKA. Subjects randomized to the ciNPT treatment arm will receive the placement of a Prevena™ Dressing in conjunction with ActiV.A.C.® or Prevena Plus™ 125 Therapy Units for a duration consistent with the Instructions for Use (IFU) document for the selected dressing but no shorter than five days post-surgery. Subjects randomized to the SOC treatment arm will receive Aquacel® Ag Surgical incision dressing, or another equivalent silver-impregnated dressing, up to the maximum number of days specified in the IFU but no shorter than five days post-surgery, not inclusive of other negative pressure wound therapy devices or dressings for the duration of the study.

Subjects will be seen during Screening (no more than 30 days before TKA revision) at the TKA revision, at weekly study treatment visits (a minimum of 5 days to a maximum number of days indicated in the Instruction for Use document for the selected dressing), the Midterm Follow-up visit (day 30 to 45), the Long Term Follow-up visit (day 90 to 104), or as initiated by either the Investigator or the subject (Unscheduled). All subjects will be followed for 90 days for outcomes regardless of the treatment received.

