4.4. Subject Withdrawal or Termination

4.4.1. *Reasons for Withdrawal or Termination*

Subjects may withdraw from participation in the study at any time upon request.

The Investigator may choose to terminate participation of the subject from the study with or without their consent for any of the following reasons:

- Adverse events
- Noncompliance
- For any reason that may, in the opinion of the Investigator, negatively affect the safety or well-being of the subject.

An Investigator must terminate participation of a subject from the study for any of the reasons indicated in section 4.15.

4.4.2. *Handling of Withdrawal or Termination*

Every effort should be made to assess SSCs and adverse events prior to the subject withdrawal. If a subject does not return for a scheduled visit, every effort should be made to contact the subject.

For subjects who are lost to follow-up, the Investigator will make attempts to collect at least the vital status (e.g., whether the subject is alive) before formally withdrawing the subject from the study. Prior to considering a subject lost to follow-up at least two documented attempts should be made to contact the subject through all available routes, and a certified letter should be sent to the permanent address on file.

Once the subject withdraws from the study, no further study evaluations will be performed, and no additional data will be collected. The Investigator may retain and continue to use any data collected before withdrawal. The subject will not be replaced.

If for any reason the subject is withdrawn by the Investigator from this study, the Investigator will inform the subject and KCI.

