4.10.3.3. Documentation

The following information regarding the application of study treatments will be documented after the surgery:

- Date of removal
- SOC only
- The number of dressing replacements
- Type of dressing (if any) applied after removal of study treatment
- ciNPT only
- Replacement of therapy unit
- Number and dates of dressing replacements (Prevena™ Peel & Place™ or Prevena Plus™ Customizable™)
- Type of dressing (if any) applied after removal of ciNPT

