5.2.7. Unscheduled Visits

Outside of scheduled study visits, if the subject needs to be assessed by the Investigator for any reason, the following procedures and assessments will be performed and documented.

- SSC Assessment
- Intervention Assessment
- Healthcare Utilization Assessment
- Concomitant Medications
- AE Assessment and SAE Reporting
- End of Study (only when a subject discontinues prior to the 90-day visit)

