8. STATISTICAL CONSIDERATIONS

8.1. Endpoint Definitions for Analysis

8.1.1. Primary Endpoint – Subject Incidence SSC

The primary endpoint is the incidence of surgical site complications (SSCs) within 90 days of TKA revision in subjects treated with ciNPT as compared to standard of care surgical dressing. The SSC endpoint includes any occurrence of superficial SSI, deep SSI, dehiscence, seroma, hematoma, skin necrosis, or continued drainage as outlined in section 4.11.1. For this endpoint there are three possible outcomes:

- “Occurred”, which is assigned if the subject had one or more occurrences of any complication and the onset date of the complication was between the time of the TKA revision and not later than 90 days after;
- “No occurrences”, which is assigned if the subject had no known occurrences of a complication within 90 days of the TKA revision and was assessed at least once on or after the 90th day following the TKA revision;
- “Incomplete follow-up”, which is assigned if the subject had no occurrences of the complication within 90 days of the TKA revision and did not have an assessment at least 90 days after the date of the revision surgery.

If a subject experiences one occurrence of any of the six complications, the primary outcome will be considered “Occurred”.

For each component of the SSC, the start date of the complication will be recorded in order to calculate the number of days from the revision surgery until occurrence of the event. If the complication did not occur, the number of days will be calculated using the last assessment which confirmed the subject to be complication-free.

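### Cross-over subjects without an SSC must leave the study although 90-day follow-up is promised regardless of treatment, and no stated rule covers their missing outcomes

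*Protocol*

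**What the plan says.** Two statements govern a subject who finishes the assigned dressing and then receives the other arm's therapy.

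- Protocol 3.2, repeated in the synopsis: "All subjects will be followed for 90 days for outcomes regardless of the treatment received".
- Protocol 4.15, where no SSC has occurred: "subjects receiving cross-over therapy after completing the original study treatment (ie, therapy from the arm in which the subject was not initially treated) must withdraw". Section 4.4.1 obliges the investigator to terminate participation for any 4.15 reason. Under 4.4.2, after withdrawal "no further study evaluations will be performed, and no additional data will be collected".

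The rest follows from the definitions. Protocol 8.1.1 and SAP 4.1 class a subject as incomplete follow-up if there was no SSC and the subject "did not have an assessment at least 90 days after the date of the revision surgery". The mITT set (Protocol 8.2, SAP 5) omits such subjects, and Protocol 8.3.4 confines the primary comparison to mITT. SAP 7.3 imputes only adverse event dates and, for sensitivity analyses, pain, KOOS and PROMIS scores. SSC is not on that list.

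There are safeguards. Protocol 4.4.2 adds "Every effort should be made to assess SSCs and adverse events prior to the subject withdrawal". SAP 8.1 tabulates exclusions from mITT by reason, and SAP 8.5 reports incomplete follow-up by arm on the ITT set. SAP 8.5.1 lists a CMH test on the ITT set, and SAP 8.7.6 has an exploratory time-to-SSC analysis.

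**The concern.** A site cannot obey both 3.2 and 4.15. If 4.15 prevails, a subject's place in the primary comparison depends on a treatment decision taken after randomisation by people who know the arm, in a trial whose endpoint the investigator assesses.

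Bias arises if the arms differ in how many subjects are withdrawn or in the later risk of those withdrawn. Removing SSC-free subjects at random from one arm raises that arm's observed rate, because those removed have already passed part of the risk period. Removing subjects at high later risk lowers it.

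The trigger might also differ by arm. Protocol 4.10.3.3 foresees a record of "Type of dressing (if any) applied after removal of ciNPT". If that dressing is silver-impregnated, a literal reader of 4.15 could call it the SOC arm's therapy. The same dressing would not be cross-over for a SOC subject, whose treatment is described as "not inclusive of other negative pressure wound therapy devices or dressings for the duration of the study". The text leaves the question open.

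**Working it through.** **1. The plan's own figures.** The pooled control rate is 0.5 × 33% + 0.5 × 6.9% = 19.95%, stated as 20%. For 20% vs 10%, two-sided 0.05 and 80% power, with pooled variance:

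n = [1.960 × √(2 × 0.15 × 0.85) + 0.842 × √(0.20 × 0.80 + 0.10 × 0.90)]² / 0.10² = 199 per arm, as stated.

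The 440 subjects less 5% loss leave 440 × 0.95 / 2 = 209 per arm. At the final level of 0.048, power is 81.4% with 209 per arm and 79.3% with 198 (10% loss). No sample-size figure is in dispute.

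**2. What happens to the subject.** An exit assessment before Day 90 can find an SSC, but it cannot produce a 'No occurrences' result, which requires an assessment on or after Day 90. The subject leaves mITT. The mPP set already exists to remove 4.15 therapy, but it is nested in Per-Protocol, which is nested in mITT. Once 4.15 is enforced, the mPP exclusion has nothing left to remove for these subjects.

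**3. Effect on the observed rate.** Let p be an arm's true 90-day rate, x the share withdrawn SSC-free and r their later risk. The observed rate is

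q = (p − x·r) / (1 − x), so q > p when r < p.

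If withdrawal is unrelated to prognosis and a share s of SSCs precedes it, r = p(1 − s) / (1 − p·s). With p = 0.20, s = 0.3 gives r = 0.149 and s = 0.7 gives r = 0.070.

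**4. Error rates with no true effect.** Assumptions: 20% in both arms, 209 per arm, withdrawal from ciNPT only (leaving 199 at 5%, 188 at 10%), unstratified pooled z test at 0.048 (critical value 1.977), interim look ignored. The documents give no values for x, s or r.

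Example, x = 0.10 and r = 0.070: q = (0.20 − 0.0070) / 0.90 = 0.2145. The pooled rate is 0.2069, the null standard error 0.0407 and the actual standard error 0.0408. P(false loss) = 1 − Φ[(1.977 × 0.0407 − 0.0145) / 0.0408] = 5.3%.

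| Withdrawn (ciNPT only) | Later risk r | Observed ciNPT rate | False ciNPT win | False ciNPT loss |
|---|---|---|---|---|
| 0% | – | 20.0% | 2.4% | 2.4% |
| 5% | 14.9% to 7.0% | 20.3% to 20.7% | 2.0% to 1.6% | 2.8% to 3.6% |
| 10% | 14.9% to 7.0% | 20.6% to 21.5% | 1.7% to 1.0% | 3.3% to 5.3% |
| 5% | 40% to 60% | 18.9% to 17.9% | 4.4% to 7.5% | 1.2% to 0.6% |
| 10% | 40% to 60% | 17.8% to 15.6% | 7.8% to 20.3% | 0.5% to 0.1% |

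If 10% leave both arms at equal later risk, each error stays at 2.4%, so there is no bias.

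**5. Power for 10% vs 20%.** It is 81.4% with no cross-over withdrawal. With ciNPT-only withdrawal unrelated to prognosis (r = 0.072 to 0.032 at p = 0.10), it is 79.0% to 77.0% at 5% withdrawn and 76.1% to 71.5% at 10%.

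**6. Why the ITT test needs a counting rule.** Take 220 per arm with 11 missing in each and 42/209 SOC vs 21/209 ciNPT among completers. Completers give p = 0.0041, and counting the missing as no SSC gives p = 0.0043. With no missing SOC subject counted as an SSC, counting 6 of the 11 missing ciNPT subjects gives p = 0.049, which no longer meets 0.048.

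**The case against.** **A sensitivity analysis is named.** A reader might infer that none is planned for missing SSC outcomes. That goes too far. SAP 8.5.1 lists an ITT CMH test among analyses labelled as sensitivity analyses, and ITT differs from mITT by exactly the subjects with incomplete follow-up. What stands is narrower. The list is introduced as optional, although the bullet itself is worded as firm, and nothing says how a missing outcome is counted. Protocol 8.3.1 and SAP 7.1 give general denominator conventions for percentages, but these do not expressly govern the test.

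**The time-to-SSC analysis uses partial follow-up.** If withdrawal is unrelated to prognosis, censoring is adequate and this analysis handles that scenario. It is exploratory, and it does not help if those withdrawn differ in later risk.

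**The scope is limited.** The cross-over rule applies only without an SSC, any SSC recorded earlier still counts, and drainage at dressing removal may already be one.

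**The arm difference is one reading.** A reader might infer that the rule removes ciNPT subjects by design. Section 4.10.3.3 records post-removal dressings in both arms, and nothing says that a routine silver dressing after completed ciNPT is cross-over. This is an ambiguity to settle, not evidence of unequal withdrawal.

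**Deep SSI.** A reader might also infer that deep SSI lacks a classification rule after withdrawal. Protocol 8.1.2.2 and SAP 4.2.2 refer it to the primary endpoint's method, which gives incomplete follow-up when no deep SSI was recorded.

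**Conclusion.** The contradiction between 3.2 (and the synopsis) and 4.15 is certain. So is the consequence under 4.4.2 and the mITT definition: later SSC outcomes of cross-over subjects withdrawn before Day 90 are lost to the primary comparison, with no stated rule for handling them.

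The size and direction of any bias cannot be derived from the documents. If withdrawal is unrelated to prognosis, the effect is small at 5% withdrawn from one arm (false loss 2.8% to 3.6% against 2.4%) and modest at 10% (3.3% to 5.3%). It is larger if those withdrawn carry a 40% to 60% later risk (false win 4.4% to 7.5% at 5%, 7.8% to 20.3% at 10%). These figures are illustrations on assumed inputs from an unstratified test, whereas the planned test is a stratified CMH. A reader might take them as bounds or as expected values; they are neither.

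**What to change.** For the cross-over trigger only, reconcile the synopsis and Protocol 3.2, 4.4.2 and 4.15 by separating the end of study treatment from the end of data collection:

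- Record the cross-over and its date, and continue the scheduled SSC and adverse event assessments through Day 90 unless consent is withdrawn.
- Analyse these subjects as randomised in the primary mITT analysis, and leave cross-over to the existing mPP exclusion.
- State in 4.15 whether a silver dressing after ciNPT removal counts as cross-over.
- Reconcile Protocol 7.7, which stops adverse event reporting at an undefined alternative therapy (except serious events assessed as related), with this follow-up.
- Add to the SAP an ITT sensitivity analysis for SSC outcomes still missing, for example a tipping-point analysis over the later risk in each arm.

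The 4.15 rules on later incision surgery and repeat revision stay outside this change. Extending it to them would count complications after a second operation in the primary endpoint, which is a separate and debatable choice. No rule on which therapy or surgery a subject may receive is proposed.

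The cost is a protocol amendment with IRB submission, SAP wording and slightly more data collection at visits already scheduled. Outcomes after cross-over may mildly dilute the contrast, follow-up rules will differ before and after the amendment, and subjects already withdrawn may not be recoverable.

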4.16. End of Study

Subjects may withdraw or be discontinued from this study at any time (Section 4.4.1). The Investigator may discontinue a subject's study participation if the Investigator feels it is in the best interest of the subject. Subjects who consent to participate in the study but do not satisfy the inclusion and exclusion criteria will be considered screen failures.

The following information will be documented:

- Date of study termination
- Completion of the study (yes/no)
- Primary reason for discontinuation

5. VISIT SCHEDULE AND DESCRIPTION OF STUDY VISITS

5.1. Schedule of Visits

	Screening	TKA Revision		End of Treatment	Midterm Follow-up	Long Term Follow-up	Unscheduled
		Pre	Post				
	Day -30 to 0	Day 0	Day 0	Per Dressing IFU	Day 30-45	Day 90 (+14 days)	
Informed Consent	X						
Pre-Operative Inclusion & Exclusion Criteria	X						
Demographics & Subject Characteristics	X						
Vital Signs	X	X ²					
Medical & Surgical History	X	X ³					
Laboratory Assessment for Pregnancy ¹	X	X					
Intra-operative Inclusion & Exclusion Criteria			X				
TKA Revision Procedure			X				
Randomization			X				
Application of Study Treatment			X				
Removal of Study Treatment				X			
SSC Assessment				X	X	X	X
Intervention Assessment				X	X	X	X
Pain Assessment		X	X ⁴	X			
Patient-Reported Outcomes Assessments (KOOS and PROMIS Global-10)	X			X	X	X	
Healthcare Utilization Assessment				X	X	X	X
End of Study						X	X ⁵
Concomitant Medications	X	X	X	X	X	X	X
Adverse Event Assessment and SAE Reporting			X	X	X	X	X

1 - Assessed on women of child-bearing potential
2 - Weight only
3 - Updates to medical and surgical history to be documented.
4 - Pain will be assessed at the earlier of discharge or 24 hours (± 2 hours) after the TKA Revision.
5 - End of Study assessed at an unscheduled visit only when a subject discontinues prior to the 90-day visit.

5.2. Description of Study Visits

5.2.1. Screening/ Day -30 to 0

The following procedures and assessments will be performed and documented.

- Informed Consent
- Pre-Operative Inclusion and Exclusion Criteria
- Demographics and Subject Characteristics
- Vital Signs
- Medical and Surgical History
- Laboratory Assessment for Pregnancy
- PRO Assessments (KOOS and PROMIS Global-10)
- Concomitant Medications

5.2.2. TKA Revision – Pre-Surgery/ Day 0

The following procedures and assessments will be performed and documented.

If Screening Visit occurs prior to Day 0:

- Vital Signs
- Medical and Surgical History
- Laboratory Assessment for Pregnancy
- Concomitant Medications

For all subjects regardless of timing of Screening Visit:

- Pain Assessment

5.2.3. TKA Revision – Post-Surgery/ Day 0

- Intra-Operative Inclusion and Exclusion Criteria Evaluation
- TKA Revision Procedure

- Randomization to either the ciNPT arm or the SOC arm (in operating room [OR])
- Application of Study Treatment
- Pain Assessment – assessed at the earlier of discharge or 24 hours (\pm 2 hours) after the TKA revision
- Concomitant Medications
- AE Assessment and SAE Reporting

5.2.4. Weekly Visit (Study Treatment Visits)

The following procedures and assessments will be performed and documented.

- Removal of Study Treatment
- SSC Assessment
- Intervention Assessment
- Pain Assessment
- PRO assessments (KOOS and PROMIS Global-10)
- Healthcare Utilization Assessment
- Concomitant Medications
- AE Assessment and SAE Reporting

5.2.5. Midterm Follow-up/Day 30 to 45

The following procedures and assessments will be performed and documented.

- SSC Assessment
- Intervention Assessment
- PRO assessments (KOOS and PROMIS Global-10)
- Healthcare Utilization Assessment
- Concomitant Medications

- AE Assessment and SAE Reporting

